	
9. Subject has acute or chronic renal disease defined as serum creatinine of >2.5 mg/dL or >220 umol/L, unless on dialysis.
 
10. Subject is pregnant or nursing.
 
11. Subject is participating in another research study involving an investigational agent (pharmaceutical, biologic, or medical device) that has not reached the primary endpoint.
 
12. Subject has other medical, social or psychological problems that, in the opinion of the investigator, preclude them from receiving this treatment, and the procedures and evaluations pre- and post-treatment.
 
13. The planned use of specialty balloons, re-entry or atherectomy devices in the target lesion(s).
 
Angiographic Exclusion Criteria
 
14. In-stent restenosis within 10mm of the target zone.
 
15. Target lesions distal to the popliteal artery.
 
16. Evidence of aneurysm or thrombus in target vessel.
 
17. No calcium or mild calcium in the target lesion.
 
18. Target lesion within native or synthetic vessel grafts.
 
19. Subject has more than three target lesions requiring treatment.
 
20. Subject has significant non-target lesion (>50% stenosis or occlusion) within the target limb (e.g. iliac, common femoral or below-the-knee) not successfully treated prior to treatment of the target lesions.
 
21. Failure to successfully cross the guidewire across the target lesion; successful crossing defined as tip of the guidewire distal to the target lesion in the absence of flow limiting dissections or perforations.

Study Statistical Methods:	Descriptive statistics will be reported.
Study Sponsor/Study Management Contact:	
Shockwave Medical, Inc. [name] [name] USA
 
Contact: [name] Title: Senior Director, Clinical Affairs Telephone: (direct): [contact] Email: [contact]

	No.: CP 64007	REV. D
	TITLE: Disrupt PAD+ Study	
	CLASS: CLINICAL PROTOCOL	PAGE 10 OF 57

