5.2 Secondary Endpoint(s)

Performance

- IVL Technical success is defined as residual stenosis $\leq 30\%$ without flow-limiting dissection (\geq Grade D) of the lesion post-IVL by angiographic core lab.
- Procedural success is defined as final residual stenosis $\leq 30\%$ without any flow-limiting dissection (\geq Grade D) in all target lesions by angiographic core lab.

Safety

- MAE at 6 and 12 months

Patency

- Primary patency at 12 months defined as freedom from clinically-driven target lesion revascularization (TLR) and freedom from restenosis determined by duplex ultrasound or angiogram $\geq 50\%$ stenosis. Acute PTA failure requiring a stent of the target lesion at any time during the index procedure will be counted as a loss of primary patency.
- Clinically driven target lesion revascularization (TLR) at 30 days, 6 and 12 months

Clinical

- Ankle-brachial index (ABI) at 12 months, reported as change from baseline
- Rutherford Category at 30 days, 6 and 12 months, reported as change from baseline

	No.: CP 64007	REV. D
	TITLE: Disrupt PAD+ Study	
	CLASS: CLINICAL PROTOCOL	PAGE 14 OF 57

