7.2 Subject Selection

7.2.1 Inclusion Criteria

General Inclusion Criteria

1. Subject is able and willing to comply with all assessments in the study.
2. Subject or subject's legal representative have been informed of the nature of the study, agrees to participate and has signed the approved consent form.
3. Age of subject is > 18.
4. Rutherford Clinical Category 2, 3, 4 or 5 of the target limb(s).
5. Estimated life expectancy >1 year.
6. Subject is intended to undergo treatment with Shockwave M⁵⁺Peripheral IVL System for de novo lesions of the ilio-femoropopliteal arteries.

Angiographic Inclusion Criteria

7. Single or multiple de novo target lesion(s) located from the common iliac to the femoropopliteal artery, in one or both limbs.
8. Target lesion reference vessel diameter is between 3.5mm and 10.0mm by visual estimate.
9. Target lesion is ≥70% stenosis by investigator via visual estimate.
10. Target lesion length is ≤200mm for lesions 70-99% stenosed. Target lesion can be all or part of the 200mm treated zone.

	No.: CP 64007	REV. D
	TITLE: Disrupt PAD+ Study	
	CLASS: CLINICAL PROTOCOL	PAGE 16 OF 57

11. Chronic total occlusion, lesion length is ≤ 100 mm of the total ≤ 200 mm target lesion.
12. Subject has at least one patent tibial vessel on the target leg with runoff to the foot, defined as no stenosis $> 50\%$.
13. Calcification is at least moderate defined as presence of fluoroscopic evidence of calcification: 1) on parallel sides of the vessel and 2) extending $> 50\%$ the length of the lesion if lesion is ≥ 50 mm in length; or extending for minimum of 20mm if lesion is < 50 mm in length.

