9.0 DATA ANALYSIS PLAN

9.1 General Statistical Methods

Descriptive statistics will be provided in this study. Analyses will be conducted at pre-specified time points including 30 days, 6 and 12 months.

Categorical data will be summarized using frequency tables, presenting the subject counts and percentages. McNemar's chi-square may be used to assess within-subject changes in a bivariate response variable.

Continuous variables will be summarized by the mean, standard deviation, median, minimum and maximum. Within-subject changes will be analyzed parametrically using the Paired t-test if the differences are normally distributed, or non-parametrically using the Sign-Rank Test if the differences are not normally distributed.

Exact confidence intervals will be generated for estimates of proportions. Asymptotic confidence intervals will be generated for estimates of means. The p-values of all tests will be reported without any correction for the multiplicity of tests performed.

Statistical analyses will be performed using SAS System® Version 9.4. Analyses will be performed on all subjects enrolled in the study cohort.

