	TITLE: Disrupt PAD+ Study	
	CLASS: CLINICAL PROTOCOL	PAGE 43 OF 57

Anemia: Decrease from baseline in red blood cells, hemoglobin, or total blood volume that is associated with hemodynamic changes or requires transfusion, or a drop in hematocrit to below 30%. Any documented anemic event requiring ≥ 2 units PRBCs will be considered an SAE.

Angina: A tight or heavy feeling in the chest, discomfort which spreads from the chest to the arm, back, neck, jaw, or stomach, numbness or tingling in the shoulders, arms or wrists, shortness of breath, and nausea relieved by rest or nitroglycerin.

Angina, unstable: Chest pain that increases in frequency, intensity, or duration, which occurs at rest, or which is new in onset. Unstable angina is a syndrome that is intermediate between stable angina and myocardial infarction: it is characterized by an accelerating or "crescendo" pattern of chest pain that lasts longer than stable angina, occurs at rest or with less exertion than stable angina, or is less responsive to medication. Unstable angina and myocardial infarction are considered acute coronary syndromes.

Ankle / Brachial Index (ABI): The ratio of systolic blood pressure measured at the ankle to systolic blood pressure measured at the brachial artery.

Arterial Occlusion / Thrombosis at Puncture Site: Angiographic or ultrasonographic evidence of occlusion at the puncture site limiting antegrade flow to the distal limb.

Arterial Perforation/Rupture/Puncture of an Arterial Wall: Classified as follows:

Angiographic perforation: Perforation detected by the clinical site at any point during the procedure.

Clinical perforation: Perforation requiring additional treatment (including efforts to seal the perforation), or resulting in significant extravasation of blood from the site, abrupt closure, limb ischemia or death.

Arterial Pseudoaneurysm: Disruption of arterial wall confirmed by imaging study and requiring intervention.

Arteriovenous Fistula (AVF): An abnormal passage or communication between an artery and a vein which may be due to the percutaneous introduction of ancillary devices (e.g., needles, catheters, guide wires) confirmed by imaging studies.

Atypical Chest Pain: Located under the sternum, left chest, abdomen, back, or arm and is fleeting or sharp. It is unrelated to exercise, not relieved by rest or the administration of nitroglycerin.

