- Hemorrhagic Stroke: neurologic deficit meeting the study definition for Stroke that is attributed to bleeding into brain tissue, epidural, subdural, or subarachnoid space; or a combination of these sites.

Target Lesion Revascularization, Clinically-driven (TLR):

A target lesion revascularization performed due to target lesion diameter stenosis $\geq 50\%$ and either evidence of clinical or functional ischemia (e.g., recurrent/progressive life-limiting intermittent claudication, claudication unresponsive to medical therapy, CLI) or recurrence of the clinical syndrome for which the initial procedure was performed. Clinically driven target lesion revascularization occurs in the absence of protocol directed surveillance ultrasound or angiography.

Target Vessel Revascularization, Clinically-driven (TVR), non-TLR: A target vessel revascularization performed due to non-target lesion diameter stenosis $\geq 50\%$ and either evidence of clinical or functional ischemia (e.g., recurrent/progressive life-limiting intermittent claudication, claudication unresponsive to medical therapy, CLI) or recurrence of the clinical syndrome for which the initial procedure was performed. Clinically driven target vessel revascularization occurs in the absence of protocol directed surveillance ultrasound or angiography.

Total Occlusion A 100% stenotic lesion as documented by angiographic absence of flow.

Thrombocytopenia: A persistent decrease in the number of blood platelets to subnormal levels.

Thrombus: Blood clot that obstructs a blood vessel.

Transient Ischemic Attack (TIA): Focal neurologic abnormalities of sudden onset and brief duration (i.e., lasting less than 24 hours and, if an imaging study is performed, shows no evidence of infarction).

Toe / Brachial Index (TBI): The ratio of systolic blood pressure measured at the toe to systolic blood pressure measured at the brachial artery.

Unanticipated Adverse Device Effect (UADE): An Unanticipated Adverse Device Effect (UADE) is defined as any serious adverse effect on health or safety or any life-threatening problem or death caused by or associated with the device, if that adverse effect, problem, or death was not previously identified in nature, severity, or degree of incidence in the protocol or application (including a supplementary plan or application), or any other unanticipated serious problem associated with a device that relates to the rights, safety, or welfare of subjects.

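### The interval for the mean ABI change should be t-based, and the plan needs a named limb, a unit of analysis and a rule for non-compressible readings (minor)

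*Combined protocol and SAP*

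**What the plan says.** Section 5.2 gives the endpoint as "Ankle-brachial index (ABI) at 12 months, reported as change from baseline". Section 15.1 defines the ABI as "The ratio of systolic blood pressure measured at the ankle to systolic blood pressure measured at the brachial artery", with no upper limit of validity and no flag for vessels that the cuff cannot compress.

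On analysis, Section 9.1 states "Continuous variables will be summarized by the mean, standard deviation, median, minimum and maximum". Proportions get exact intervals, but for means "Asymptotic confidence intervals will be generated for estimates of means". Within-subject changes are tested by paired t-test, or by the signed-rank test if the differences are not normal, and all enrolled subjects are analysed. Section 9.2 promises a two-sided 95% interval for every endpoint. Section 6.2 caps enrolment at 40 subjects, and Section 9.4 rules out imputation for the primary analyses.

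On population, inclusion criterion 13 in Section 7.2.1 reads "Calcification is at least moderate defined as presence of fluoroscopic evidence of calcification". Exclusion 9 bars "serum creatinine of >2.5 mg/dL or >220 umol/L, unless on dialysis", so dialysis patients may enter. Criterion 7 allows "Single or multiple de novo target lesion(s) located from the common iliac to the femoropopliteal artery, in one or both limbs". Neither the endpoint, Table 1 nor Section 9.1 says which limb supplies the ABI, or whether the unit is the limb or the subject.

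Section 15.1 also defines a toe-brachial index ("The ratio of systolic blood pressure measured at the toe to systolic blood pressure measured at the brachial artery"), but it is not an endpoint and appears neither in Table 1 nor in any visit list.

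**The concern.** There are two separate issues.

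**Interval.** A paired t-test on n differences uses a t quantile on n−1 degrees of freedom. An asymptotic interval for the same mean would normally use 1.960. The interval then falls short of its nominal coverage and can exclude zero when the test does not reach 5%. Section 9.1 takes care to be exact for proportions, so the choice for means looks like an oversight.

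**Validity of the readings.** If a stiff, calcified ankle artery resists the cuff, the ABI reads high and no longer follows flow. A study that selects for calcified lesions and admits dialysis patients can reasonably expect some such readings. With no rule fixed in advance, they enter the mean change, or someone decides after seeing the data whether they stay. The study is single-arm, so no control group would share the artefact.

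At stake is the estimate and interval for one secondary endpoint. The primary endpoints and the sample size are unaffected.

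**Working it through.** **The plan's own figure.** The only precision figure is in Section 9.2: 65% success in 40 lesions, interval [48.3, 79.4]. The Clopper-Pearson interval for 26/40 is [48.3, 79.4], which reproduces it. The Wald interval is [50.2, 79.8] and does not. The plan therefore used the exact method it names for proportions. It gives no figure for ABI.

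**Normal versus t quantile.** Inputs: two-sided 95% (Section 9.2); at most 40 subjects (Section 6.2); fewer with a 12-month ABI if any are lost. For normal differences, the true coverage of the normal-quantile interval is 1 − 2·P(T[n−1] > 1.960), and its width relative to the t-interval is 1.960/t[0.975, n−1].

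| n | t quantile | too narrow by | true coverage |
|---|---|---|---|
| 40 | 2.023 | 3.1% | 94.3% |
| 30 | 2.045 | 4.2% | 94.0% |
| 20 | 2.093 | 6.4% | 93.5% |

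With an assumed SD of 0.20 and n=40, the half-width is 1.960 × 0.20/√40 = 0.062 with the normal quantile and 2.023 × 0.20/√40 = 0.064 with t. Interval and test disagree only when the t statistic lies between 1.960 and 2.023, that is, for a mean change between 0.062 and 0.064. At an assumed change of 0.20 the t statistic is 0.20/(0.20/√40) = 6.3, far outside that band.

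**Non-compressible readings.** The documents give no expected change, no SD and no share of such readings. Assumptions: change d = 0.20 and SD 0.20 in compressible readings; mean change 0 in the others, with SD 0.20 or 0.40; share f from 5% to 30%.

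- Mean = (1−f) × 0.20.
- Variance = (1−f)(0.20² + 0.20²) + f·s² − mean², where s is the SD of the affected readings. For f = 10% and s = 0.40: 0.9 × 0.08 + 0.1 × 0.16 − 0.18² = 0.0556, so the SD is 0.236.

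| f | mean | SD (s=0.20) | SD (s=0.40) | t half-width at n=40 (s=0.20 / s=0.40) |
|---|---|---|---|---|
| 0 | 0.20 | 0.200 | 0.200 | 0.064 / 0.064 |
| 5% | 0.19 | 0.205 | 0.219 | 0.065 / 0.070 |
| 10% | 0.18 | 0.209 | 0.236 | 0.067 / 0.075 |
| 20% | 0.16 | 0.215 | 0.265 | 0.069 / 0.085 |
| 30% | 0.14 | 0.220 | 0.291 | 0.070 / 0.093 |

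A single spurious change of 1.0 moves the mean by 1.0/40 = 0.025.

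**Unit of analysis.** If limbs were the unit and 25% of 40 subjects (assumed) contributed two, there would be 30 + 20 = 50 limbs. The variance inflation is 1 + (Σm²/Σm − 1)ρ, where m is the number of limbs per subject and ρ the within-subject correlation. Here Σm²/Σm = (30 + 40)/50 = 1.4, so the inflation is 1.12 at ρ = 0.3 and 1.28 at ρ = 0.7 (assumed range). Ignoring it makes the interval 1 − 1/√1.12 = 5.5% to 1 − 1/√1.28 = 11.6% too narrow, more than the quantile effect at 30 to 40 subjects.

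**The case against.** The case for leaving the plan alone is fair on several counts.

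- The endpoint is descriptive, with no success criterion. The quantile effect is 0.002 ABI units under the assumed SD, and Section 9.1 never names a normal quantile. This stands: the interval point is small, and it depends on the natural reading of asymptotic.
- A reader might infer that the plan averages ABI over all limbs. The documents do not say so. Section 9.1 speaks of subjects and within-subject changes. The defect is that limb and unit are not stated.
- A reader might also infer that non-compressible readings are bound to distort the result. The required calcification is in the iliac-to-popliteal target lesion, exclusion 15 bars target lesions below the popliteal artery, and no passage describes the ankle arteries or gives an expected number on dialysis. Involvement at the ankle is a clinical inference. Section 3.1, which links peripheral disease to system-wide atherosclerosis, makes it plausible but supplies no frequency.
- The median, minimum and maximum are reported beside the mean, and the signed-rank test is available, so extreme values would be visible. This stands in part, because the mean and its interval remain unprotected.
- An artefact present at both visits would partly cancel in a change score, so the larger assumed SD of 0.40 may be pessimistic.

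The absence of any rule for such readings, and the mismatch between interval and test, are not answered by these points.

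**Conclusion.** The point holds as a minor one. If asymptotic means a normal quantile, the nominal 95% interval for the mean ABI change covers about 94.3% at n=40 and 94.0% at n=30, is 3% to 4% too narrow, and can differ from the paired t-test in a narrow band of results. This rests on normal differences and on the subject as the unit.

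The lack of a rule for non-compressible readings is a real gap of unknown size. The means of 0.19 to 0.14 are illustrations under an assumed change of 0.20 and assumed shares of 5% to 30%. In that model the bias is always toward zero, and the share determines only how large it is. The documents do not support a claim that such readings will be common or that the ABI result will be materially wrong.

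**What to change.** In Section 9.1:

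1. Replace the asymptotic interval for means with a t-based interval, and give a Hodges-Lehmann interval where the signed-rank test is used.
2. State that the ABI is that of the target limb, and whether the unit is the limb or the subject. If limbs are the unit, account for clustering within subject.
3. Fix in advance a cut-off for flagging an ABI reading as non-compressible, and report the count at each visit.
4. Present the mean ABI change in those compressible at baseline beside the all-subject result. Do not exclude on the 12-month value: that selects on a post-treatment outcome, and removing high follow-up readings can bias the mean change downward.

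The cost is wording only, with no new visit or measurement. The downside is a slightly smaller n in the restricted row. A reading that becomes non-compressible only at 12 months stays in both rows, and the visit counts would show how many there are.

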6.0 STUDY DESIGN

The Disrupt PAD+ study is a prospective, multi-center, single-arm study of the M⁵⁺ Peripheral IVL System to treat calcified peripheral arteries.

6.1 Site Selection

Up to 10 sites located in Australia, New Zealand and the US will participate in the study.

6.2 Number of Subjects

A minimum of 40 lesions in up to 40 subjects with moderate and severely calcified iliac and femoropopliteal artery disease presenting with Rutherford Category 2 to 5 will be enrolled. Each site will be allowed to enroll a maximum of 12 subjects. Multiple lesion treatment with IVL will be allowed and a minimum of twenty (20) lesions across all enrolled subjects must be treated with the 8.0 mm catheter size.

6.3 Clinical Study Duration

Enrollment is anticipated to last approximately 6 months. Study subjects will be followed through hospital discharge, 30 days, and 6 and 12 months post-procedure. Duplex ultrasound (DUS) assessments will be completed at 12 months. Total anticipated study duration is 18 months.

	No.: CP 64007	REV. D
	TITLE: Disrupt PAD+ Study	
	CLASS: CLINICAL PROTOCOL	PAGE 15 OF 57

7.0 STUDY PROCEDURES

7.1 Screening

Patients presenting to the institution with known iliac and/or femoropopliteal disease requiring an interventional procedure will be evaluated for eligibility and participation in the study. A member of the participating site's study team will perform an initial evaluation of the potential participant's medical history and previously performed examinations to assess for initial eligibility. Pre-procedure imaging (DUS, angiogram, CTA, MRA) should be performed according to the institution's standard of care.

Potential subjects will be screened for eligibility. Written informed consent will be obtained prior to any study-specific requirements. A potential subject will be informed of the elements of the study including risks, potential benefits, and required follow-up procedures prior to obtaining the potential subject's informed consent.

Subjects who meet the clinical inclusion/exclusion criteria will undergo an angiogram. At the time of the angiogram, the subject is considered enrolled if all angiographic eligibility criteria are met, and the M⁵⁺ peripheral IVL catheter is inserted into the patient. A subject is considered an angiographic screen failure if they do not meet angiographic eligibility. Patients who screen failed will be documented as such in the electronic data capture (EDC) system.

7.2 Subject Selection

7.2.1 Inclusion Criteria

General Inclusion Criteria

1. Subject is able and willing to comply with all assessments in the study.
2. Subject or subject's legal representative have been informed of the nature of the study, agrees to participate and has signed the approved consent form.
3. Age of subject is > 18.
4. Rutherford Clinical Category 2, 3, 4 or 5 of the target limb(s).
5. Estimated life expectancy >1 year.
6. Subject is intended to undergo treatment with Shockwave M⁵⁺Peripheral IVL System for de novo lesions of the ilio-femoropopliteal arteries.

Angiographic Inclusion Criteria

7. Single or multiple de novo target lesion(s) located from the common iliac to the femoropopliteal artery, in one or both limbs.
8. Target lesion reference vessel diameter is between 3.5mm and 10.0mm by visual estimate.
9. Target lesion is ≥70% stenosis by investigator via visual estimate.
10. Target lesion length is ≤200mm for lesions 70-99% stenosed. Target lesion can be all or part of the 200mm treated zone.

	No.: CP 64007	REV. D
	TITLE: Disrupt PAD+ Study	
	CLASS: CLINICAL PROTOCOL	PAGE 16 OF 57

11. Chronic total occlusion, lesion length is ≤ 100 mm of the total ≤ 200 mm target lesion.
12. Subject has at least one patent tibial vessel on the target leg with runoff to the foot, defined as no stenosis $> 50\%$.
13. Calcification is at least moderate defined as presence of fluoroscopic evidence of calcification: 1) on parallel sides of the vessel and 2) extending $> 50\%$ the length of the lesion if lesion is ≥ 50 mm in length; or extending for minimum of 20mm if lesion is < 50 mm in length.

7.2.2 Exclusion Criteria

General Exclusion Criteria

1. Rutherford Clinical Category 0, 1 and 6.
2. Subject has active infection requiring antibiotic therapy.
3. History of endovascular or surgical procedure on the target limb within the last 30 days or planned within 30 days of the index procedure. *Note: Concomitant IVL treatment to facilitate large bore access at the time of procedure is allowed.*
4. Subject in whom antiplatelet or anticoagulant therapy is contraindicated.
5. Subject has known allergy to contrast agents or medications used to perform endovascular intervention that cannot be adequately pre-treated.
6. Subject has known allergy to urethane, nylon, or silicone.
7. Myocardial infarction within 60 days prior to enrollment.
8. History of stroke within 60 days prior to enrollment.
9. Subject has acute or chronic renal disease defined as serum creatinine of > 2.5 mg/dL or > 220 $\mu\text{mol/L}$, unless on dialysis.
10. Subject is pregnant or nursing.
11. Subject is participating in another research study involving an investigational agent (pharmaceutical, biologic, or medical device) that has not reached the primary endpoint.
12. Subject has other medical, social or psychological problems that, in the opinion of the investigator, preclude them from receiving this treatment, and the procedures and evaluations pre- and post-treatment.
13. The planned use of specialty balloons, re-entry or atherectomy devices in the target lesion(s).

Angiographic Exclusion Criteria

14. In-stent restenosis within 10mm of the target zone.
15. Target lesions distal to the popliteal artery.
16. Evidence of aneurysm or thrombus in target vessel.
17. No calcium or mild calcium in the target lesion.
18. Target lesion within native or synthetic vessel grafts.

	No.: CP 64007	REV. D
	TITLE: Disrupt PAD+ Study	
	CLASS: CLINICAL PROTOCOL	PAGE 17 OF 57

19. Subject has more than three target lesions requiring treatment.

20. Subject has significant non-target lesion (>50% stenosis or occlusion) within the target limb (e.g. iliac, common femoral or below-the-knee) not successfully treated prior to treatment of the target lesions.

21. Failure to successfully cross the guidewire across the target lesion; successful crossing defined as tip of the guidewire distal to the target lesion in the absence of flow limiting dissections or perforations.

